5.3. Secondary objective

5.3.1. Analysis of secondary objective planned in the protocol

The incidence rate of first AFI due to LCD by serotype (DENV 1 – 4) and incidence rate of AFI due to non-LCD with 95% exact confidence interval will be calculated for overall and age group (could you please put here the age categories?).

Description of signs and symptoms of AFI due to LCD and due to non-LCD will include the percentage of AFI presenting each sign or symptom (any intensity and grade 3) during the 7-day period from the onset of fever (body temperature 38°C/100.4°F). The sign or symptom of suspected dengue infection is summarized in Table 1. Duration of signs and symptoms will also be described for LCD and non-LCD episodes. Analysis will be done overall and then separately by age group.

Table 1 Solicited symptoms of suspected dengue infection

Signs and symptoms
body temperature and route (minimum of two measurements)
headache / irritability
eye pain
myalgia (muscle pain)
arthralgia (joint pain)
abdominal pain
nausea
vomiting
rash
any bleeding (skin, mouth, anus)
loss of appetite
Fatigue/decrease in normal activity
reduced fluid intake

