9.6. Analysis of primary and secondary objectives

The following analyses will be performed:

- Computation of incidence rate of AFI due to LCD and due to non-LCD with 95% CI: the numerator will be the number of subjects with AFI due to LCD and due to non-LCD during the study period. The denominator will be the total person-years at risk.
- Description of signs and symptoms of AFI due to LCD and due to non-LCD will include the percentage of AFI presenting each sign or symptom (any intensity and grade 3) during the 7-day period from the onset of fever (body temperature $\geq 38^{\circ}\text{C}/\geq 100.4^{\circ}\text{F}$). Duration of signs and symptoms will also be described for LCD and non-LCD episodes. Analysis will be done overall and then separately for episodes of AFI occurring in subjects < 5 years of age, in subjects 5 to 11 years of age, and in subjects ≥ 12 years of age.
- Computation of incidence rates of AFI due to LCD with 95% CI by type (DENV 1-4), study site and age group (6 months to 4 years, ≥ 5 years-11 years, ≥ 12 years to 17 years, ≥ 18 years): the numerator will be the number of subjects with AFI due to LCD in the category. The denominator will be the total person-years at risk in the category.

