3.5. Secondary endpoints

- Occurrence of AFI due to non-LCD.
- Occurrence and intensity of signs and symptoms of interest, during the 7-day period following the onset of each episode of AFI due to LCD and due to non-LCD.
- Occurrence of AFI due to LCD by DENV type, study site and age group.

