5.2. Primary objective

5.2.1. Analysis of primary objective planned in the protocol

The incidence rate of first AFI due to LCD will be calculated along with 95% exact confidence interval. This analysis will be based on the total enrolled set. See section 9.2.1 and section 9.2.2 for details of incident rate and confidence interval calculation respectively.

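### Does the SAP lose the protocol's dengue incidence by age group, because section 5.3.1 leaves the age bands as an open query and names no all-type rate by age?

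*SAP*

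**What the plan says.** Protocol section 9.6 sets out the secondary rate analysis: "Computation of incidence rates of AFI due to LCD with 95% CI by type (DENV 1-4), study site and age group". It gives four age bands (6 months to 4 years, 5 to 11, 12 to 17, 18 and over) and fixes the denominator: "The denominator will be the total person-years at risk in the category". For signs and symptoms the same section uses three groups: under 5 years, then episodes "in subjects 5 to 11 years of age, and in subjects ≥ 12 years of age".

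The SAP keeps the endpoint in section 3.5: "Occurrence of AFI due to LCD by DENV type, study site and age group". It then spreads the analysis over two places. Section 5.2.1 covers the all-type rate, with no age breakdown: "The incidence rate of first AFI due to LCD will be calculated along with 95% exact confidence interval". Section 5.3.1 starts from "The incidence rate of first AFI due to LCD by serotype", adds the non-LCD rate, and says that these "will be calculated for overall and age group (could you please put here the age categories". The request to supply the categories was never answered there. On symptoms, section 5.3.1 says only: "Analysis will be done overall and then separately by age group".

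The one list of age bands in the SAP text is in section 10.1.2.2: under 5, 5 to 11, 12 to 17, and 18 or over, attached to age at the time of the acute febrile illness (AFI). SAP section 8 lists omitted analyses, all of them tertiary.

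**The concern.** Read literally, SAP 5.3.1 gives LCD rates by age only within serotype, so the all-type LCD rate by age has no stated method. The study is meant to supply incidence data for sizing later vaccine trials (Protocol section 3.1), and all-type incidence by age is one of the figures a trial planner would look for.

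Three further points add to the impression of a gap:

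- The unanswered query suggests that the bands were never settled.
- The only SAP list has four groups, where the protocol has three for symptoms.
- That list is defined on age at AFI. Subjects who never had an AFI have no such age, so the list cannot by itself assign person-years to a band.

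At stake would be a missing secondary table, symptom tables in groups the protocol did not plan, or an age-specific rate whose numerator and denominator are banded differently.

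**Working it through.** **1. Do the bands conflict?** Each completed year of age falls as follows.

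| Age | Protocol 9.6, rates | SAP 10.1.2.2 | Protocol 9.6, symptoms |
|---|---|---|---|
| under 5 (entry from 6 months) | 6 months–4 | <5 | <5 |
| 5–11 | 5–11 | 5–11 | 5–11 |
| 12–17 | 12–17 | 12–17 | ≥12 |
| 18 and over | ≥18 | ≥18 | ≥12 |

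The SAP's four bands equal the protocol's four rate bands one to one, so the query is already answered in both documents. For symptoms, the SAP's last two bands together are the protocol's third group.

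**2. Is the all-type rate by age dropped?** SAP sections 3.2 and 3.5 retain it, section 8 does not list it as omitted, and section 5.3.1 is headed as the analysis planned in the protocol. Protocol 9.6 states numerator, denominator and bands. Nothing is left to invent.

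**3. Which age?** Protocol 9.4 defines age in the study as age at enrolment, which every subject has. Protocol 9.6 places cases and person-years in the same category. Enrolment age for both is the natural reading.

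**4. Size.** The plan's own figures reproduce: 60/3300 × 100 = 1.82 per 100 person-years, exact Poisson 95% CI 1.39 to 2.34; and 16/3300 × 100 = 0.48, CI 0.28 to 0.79. Both agree with Protocol Table 17.

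To see how the age tables would look, assume equal incidence at all ages and ages uniform from 0.5 to 51. The band widths are 4.5, 7, 6 and 33 of 50.5 years, which puts 17.5/50.5 = 34.7% of subjects under 18.

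- Under 5, all types: 60 × 4.5/50.5 = 5.3 cases.
- Under 5, one type: 16 × 4.5/50.5 = 1.4 cases.
- 12–17: 60 × 6/50.5 = 7.1. 18 and over: 60 × 33/50.5 = 39.2. Together 46.3, the protocol's group of 12 and over.

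If children make up 30% to 50% of the cohort, the under-5 share is 0.30 × 4.5/17.5 = 7.7% to 0.50 × 4.5/17.5 = 12.9%. That is 4.6 to 7.7 of 60 all-type cases and 1.2 to 2.1 of 16.

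The all-type cell is therefore the more useful one, and the protocol asks for it. Five cases carry an exact 95% interval of 1.62 to 11.67, that is −68% to +133%. The equal-incidence assumption is weak: Protocol 1.1 cites disease incidence above 3% per year in Colombo children, so the child counts could be higher.

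**The case for a change.** The strongest argument for a change is that a SAP should stand on its own, and this one carries an unanswered query in a secondary analysis. Taking 'overall' in 5.3.1 to mean all serotypes is strained, because it is paired with age group and also governs non-LCD illness, which has no serotype. The section also names no rate by study site, although Protocol 9.6 and SAP 3.5 both list one. All of that is correct, and it shows careless drafting. It does not show that an analysis was withdrawn or that a wrong one was put in its place.

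The other parts carry less weight.

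- **Symptoms.** The four-against-three mismatch arises only if section 10.1.2.2 is applied to symptoms, which section 5.3.1 does not say. Setting about 7 episodes at ages 12–17 against about 46 at 12 and over compares a subset with its whole. The whole is recovered by adding two columns.
- **Small serotype cells.** Wide intervals at one case, against narrower ones at five, show only that small cells are imprecise. Serotype rows can also be added to approximate the all-type count, provided serotype-specific testing is used throughout. Protocol 6.5.5.1.4 allows generic testing too.
- **Mixed banding.** Suppose cases were banded by age at AFI and undivided person-time by enrolment age. With uniform ages and full two-year follow-up, children enrolled at 0.5 to 5 give 4.5 × 2 = 9 units of person-time. Infants reaching 6 months during the study add ∫(2 − t)dt over 0 to 2 = 2 units. Time lived past the fifth birthday is ∫(a − 3)da over 3 to 5 = 2 units. The under-5 rate would read low by 2/11 = 18%. That is well inside the interval for five cases, and Protocol 9.6 already rules this reading out by tying person-years to the category.

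**Conclusion.** No change to the plan is called for. SAP 5.3.1 is an incomplete copy of Protocol 9.6 with a drafting query left in. The protocol remains in force and supplies the missing pieces: all-type LCD rates by age and by site, four rate bands, a matched denominator and three symptom groups. The SAP's own band list agrees with the rate bands, and its finer split reproduces the symptom groups by addition. If the four-group symptom version is reported, Protocol 9.10 already requires departures from the planned analysis to be described and justified in the study report.

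The effect on the overall primary rate is nil. The effect on the secondary age tables is also nil for an analyst who reads both documents. A literal programmer could leave out one table, but it could be produced from the same data at any time. Analyses are descriptive (SAP section 6) and there is no success criterion (Protocol 9.9), so no decision turns on the wording.

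This rests on two assumptions: that the SAP is applied together with the protocol, and that enrolment age is used for both parts of each age-specific rate. The table shells are held outside the documents (SAP 10.2) and could not be checked. Filling in the bands would tidy the text but would not alter a result.

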5.4. Tertiary objectives

5.4.1. Analysis of tertiary objectives planned in the protocol

- Sensitivity, specificity, positive predictive value, negative predictive and overall agreement value of NS1-antigen (ICT test) in prediction of RT-qPCR test results will be computed. Cohen's Kappa will be used to evaluate the agreement between two measures. See section 9.2.3.
- Computation of incidence rate of AFI due to dengue confirmed by NS1-antigen (ICT test and/or ELISA) with 95% CI: the numerator will be the number of subjects with AFI due to dengue confirmed by NS1-antigen (ICT test and/or ELISA) during the study period. The denominator will be the total person-years at risk.
- Computation of incidence rates of AFI due to LCD having ≥ 3 consecutive calendar days of fever (body temperature $\geq 38^{\circ}\text{C}/\geq 100.4^{\circ}\text{F}$) and incidence of AFI due to LCD resulting in hospitalisation with 95% CI.
- Frequency of symptoms associated with AFI due to LCD having ≥ 3 consecutive calendar days of fever (body temperature $\geq 38^{\circ}\text{C}/\geq 100.4^{\circ}\text{F}$) and result in hospitalization will tabulated overall and by age group. Univariate and Multivariate analyses will be done to identify categories of medically relevant signs and symptoms associated with high probability of LCD (any severity, having ≥ 3 consecutive calendar days of fever (body temperature $\geq 38^{\circ}\text{C}/\geq 100.4^{\circ}\text{F}$) and resulting in hospitalisation) *versus* non-LCD episodes using logistic regressions. See section 9.2.4.
- Computation of the frequency and percentage of the reasons of hospitalization throughout the study among all hospitalization visits.
- Calculation of the frequency and percentage of subject with other infective agent: influenza viruses, chikungunya viruses among subject with subjects with AFI.

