9.7. Analysis of tertiary (research) objectives

Some tertiary (research) analyses may be done including:

(Amended 01 March 2017)

- Neutralising antibody titres against JEV: the seropositivity rates to JEV with exact 95% CI and GMTs with 95% CI and range of antibody titres will be tabulated.
- A concordance analysis between dengue virus detection by RT-qPCR and by NS1-antigen (***ICT test***) may be performed. This analysis may be stratified by day of sampling if sufficient data are available. Sensitivity, specificity, positive predictive value and negative predictive value of NS1-antigen (***ICT test***) in prediction of RT-qPCR test results will be computed. **(Amended 01 March 2017)**
- Computation of incidence rate of AFI due to dengue confirmed by NS1-antigen (ICT test and/or ELISA) with 95% CI: the numerator will be the number of subjects with AFI due to dengue confirmed by NS1-antigen (ICT test and/or ELISA) during the study period. The denominator will be the total person-years at risk.
- Evaluation of different case definitions by:
- Computation of incidence rates of AFI due to LCD having ≥ 3 consecutive calendar days of fever (body temperature $\geq 38^{\circ}\text{C}/\geq 100.4^{\circ}\text{F}$) or incidence of AFI due to LCD resulting in hospitalisation with 95% CI.
- Descriptive analysis of the signs and symptoms associated with AFI due to LCD having ≥ 3 consecutive calendar days of fever (body temperature $\geq 38^{\circ}\text{C}/\geq 100.4^{\circ}\text{F}$) or resulting in hospitalisation.
- Multivariate analyses could be done to identify categories of medically relevant signs and symptoms associated with high probability of LCD (any severity, having ≥ 3 consecutive calendar days of fever (body temperature $\geq 38^{\circ}\text{C}/\geq 100.4^{\circ}\text{F}$) and resulting in hospitalisation) *versus* non-LCD episodes using logistic regressions and/or classification and regression tree analysis to provide support for the definition of a moderate-to-severe dengue case for future clinical endpoint trials. Same analyses may be done to identify category of signs and symptoms associated with high probability of LCD having ≥ 3 consecutive calendar days of fever (body temperature $\geq 38^{\circ}\text{C}/\geq 100.4^{\circ}\text{F}$) or resulting to hospitalisation.

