- Values of signs and symptoms in predicting LCD in AFI will be computed (sensitivity, specificity, positive predictive value and negative predictive value). Same computations may be done in predicting LCD having ≥ 3 consecutive calendar days of fever (body temperature $\geq 38^{\circ}\text{C}/\geq 100.4^{\circ}\text{F}$) or resulting to hospitalisation.
- Descriptive analysis of the spatio-temporal clustering of cases using a map of study households. Occurrence of AFI due to LCD within 2 weeks from an index case, in the same household or within 50 metres of the household of the index case will be analysed.
- Descriptive analysis of incidence and reason for hospitalisation in the study population, throughout the study period.

- Description of entomological characteristics such as vector species, vector density and breeding sites at selected site(s).

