3.3. Tertiary Objectives

- To describe DENV and Japanese Encephalitis Virus (JEV) antibody profiles in subsets of subjects with AFI.
- To assess the concordance between dengue Reverse transcriptase-quantitative Polymerase Chain Reaction (RT-qPCR) and Non-Structural protein 1 (NS1)-antigen Immuno Chroma Tographic (ICT) test and/or Enzyme-Linked Immunosorbent Assay (ELISA) in the assessment of dengue infection.
- To gather clinical data that will support the definition of clinical endpoints for future efficacy trials.
- To describe spatio-temporal clustering of LCD cases.
- To describe entomological characteristics at selected site(s).
- To estimate the prevalence and incidence of tuberculosis diagnosis in the study population.
- To describe the incidence of hospitalisation and discharge diagnosis in the study population.
- To isolate and characterise infectious agents from a subset of subjects with AFI.
- To evaluate the antibody response to infectious agents in a subset of subjects with AFI.

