3.6. Tertiary endpoints

The following is a list of planned tertiary analyses. Per protocol, tertiary study endpoint assays other than dengue serology *may be* performed for a subset of samples (for example, JEV assays will only be conducted if additional studies indicate that JEV serology is needed to interpret the DENV antibody).

Refer to section 8 for information regarding tertiary analyses that will not be performed.

- Neutralising antibody titres against DENV 1-4.
- Neutralising antibody titres against JEV.
- Neutralising antibody titres against other viruses, including but not limited to, Chikungunya virus.
- Incidence of NS1-antigen (ICT test and/or ELISA)-positive AFI by DENV type.
- Concordance between dengue RT-qPCR and NS1-antigen (ICT and/or ELISA) assays.)
- Occurrence of AFI due to LCD and due to non-LCD having ≥ 3 days of fever (body temperature $\geq 38^{\circ}\text{C}/\geq 100.4^{\circ}\text{F}$).
- Occurrence of AFI due to LCD and due to non-LCD resulting in hospitalisation.
- Occurrence of combinations of signs and symptoms during the 7-day period following the onset of each episode of AFI due to LCD and due to non-LCD.
- Occurrence of AFI due to LCD within 2 weeks from an index case, in the same household or within 50 metres of the household of the index case.
- Entomological characteristics for LCD cases (e.g., vector species, density and number of breeding sites)
- Occurrence (by medical history only) of a diagnosis of tuberculosis, from birth up to study conclusion, in the study population.
- Occurrence of hospitalisation and discharge diagnosis.
- Identification and characterisation of infectious agents isolated from blood (e.g., DENV, influenza viruses, chikungunya viruses), in subjects with AFI.

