8. CHANGES FROM PLANNED ANALYSES

Due to limitations of data (no data availability) or resources, the following tertiary objectives are omitted from the analysis.

- To describe DENV and Japanese Encephalitis Virus (JEV) antibody profiles in subsets of subjects with AFI.
- Neutralising antibody titres against DENV 1-4.
- Neutralising antibody titres against JEV.
- Neutralising antibody titres against other viruses, including but not limited to, Chikungunya virus.
- To describe spatio-temporal clustering of LCD cases.
- To describe entomological characteristics at selected site(s).
- To estimate the prevalence and incidence of tuberculosis diagnosis in the study population.
- To isolate and characterise infectious agents from a subset of subjects with AFI.
- To evaluate the antibody response to infectious agents in a subset of subjects with AFI.

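### SAP 5.4.1 specifies no incidence rate for the hospitalisation objective that the SAP retains, and no symptom predictive values, and Section 8 lists neither as dropped

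*SAP*

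**What the plan says.** **Hospitalisation.** Protocol 9.7 plans a "Descriptive analysis of incidence and reason for hospitalisation in the study population, throughout the study period". SAP 3.3 repeats the objective, "To describe the incidence of hospitalisation and discharge diagnosis in the study population", and SAP 3.6 repeats the endpoint, "Occurrence of hospitalisation and discharge diagnosis". The matching entry in SAP 5.4.1 is "Computation of the frequency and percentage of the reasons of hospitalization throughout the study among all hospitalization visits". The only hospitalisation rate in the SAP is for laboratory-confirmed dengue (LCD) cases that led to admission.

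**Symptoms as predictors of LCD.** Protocol 9.7 states: "Values of signs and symptoms in predicting LCD in AFI will be computed". It names sensitivity, specificity and the positive and negative predictive values (PPV, NPV). SAP 5.4.1 and 9.2.3 apply these measures only to the NS1 test against RT-qPCR. For symptoms, SAP 5.4.1 gives frequency tables and logistic regression.

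**Record of changes.** SAP Section 8 says that "the following tertiary objectives are omitted from the analysis" and gives nine items. Neither all-cause hospitalisation incidence nor the symptom accuracy measures are among them. SAP 3.6 sends the reader to Section 8 to learn which tertiary analyses will not be done.

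**The concern.** The SAP keeps an incidence objective but pairs it with an analysis whose denominator is hospitalisation visits. Followed as written, it produces no rate of all-cause hospitalisation in the cohort. Because Section 8 is the stated list of what is dropped and omits this item, a reader would expect the rate to appear.

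The stake is modest but real. Protocol Table 2 has hospitalisation asked about at each weekly contact, with discharge diagnosis, and documented in the eCRF. So the data for a rate are collected for every enrolled subject, subject to missed contacts and to one adult answering for the household.

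The symptom measures are the smaller matter. Protocol 9.7 places them among the analyses for evaluating case definitions. Their absence leaves that work without stated predictive values or intervals.

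**Working it through.** The plan gives no hospitalisation figure to reproduce, so the check is mainly a comparison of texts, followed by two illustrations with assumed inputs.

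**1. Matching plan to SAP**

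| Item | Protocol 9.7 | SAP analysis | SAP Section 8 |
|---|---|---|---|
| Reason for hospitalisation | planned | 5.4.1, per visit | not applicable |
| Incidence of hospitalisation, all causes | planned | none | not listed |
| Symptom sensitivity and specificity for LCD | planned | not named; derivable from 5.3.1 | not listed |
| Symptom PPV and NPV for LCD | planned | not named | not listed |
| Logistic regression on symptoms | planned as possible | 5.4.1 and 9.2.4 | not applicable |

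**2. What a visit-based table leaves open**

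Input: about 3,300 person-years (protocol 9.2). A simple check of that figure is 2000 × 0.9 + 2000 × 0.9 × 0.8 = 1800 + 1440 = 3240, within 3% of it. The hospitalisation counts below are assumptions.

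Rate = n / 3300 × 1000. Exact Poisson limits are χ²(0.025; 2n)/2 and χ²(0.975; 2(n+1))/2, each divided by 3300 and multiplied by 1000.

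| Subjects hospitalised (assumed) | Rate per 1000 person-years | 95% CI |
|---|---|---|
| 50 | 15.2 | 11.2 to 20.0 |
| 100 | 30.3 | 24.7 to 36.9 |
| 300 | 90.9 | 80.9 to 101.8 |

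Suppose the reasons table totals 100 visits. If 100 subjects were each admitted once, the first-event rate is 30.3. If 50 subjects were each admitted twice, it is 15.2. The table is identical in both cases. Person-time is held at 3,300 for simplicity. Under the 9.2.1 rule follow-up stops at the first event, so the true denominator would be slightly smaller.

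**3. What SAP 5.3.1 already supplies on symptoms**

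SAP 5.3.1 tabulates the percentage of LCD and of non-LCD episodes that show each symptom. For one symptom, let a of n1 LCD episodes and b of n0 non-LCD episodes show it.

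- Sensitivity = a/n1, the LCD percentage.
- Specificity = 1 − b/n0, the complement of the non-LCD percentage.
- PPV = a/(a + b) and NPV = (n0 − b)/[(n0 − b) + (n1 − a)]. These also need the episode counts.

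Percentages alone do not fix the PPV, because it depends on the share of tested episodes that are LCD. With assumed sensitivity 0.50 and specificity 0.80:

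- LCD share 5%: PPV = 0.50 × 0.05 / (0.50 × 0.05 + 0.20 × 0.95) = 0.025/0.215 = 0.12; NPV = 0.76/0.785 = 0.97.
- LCD share 20%: PPV = 0.10/(0.10 + 0.16) = 0.38; NPV = 0.64/0.74 = 0.86.

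So sensitivity and specificity can be read from planned output, and PPV and NPV can be calculated if counts are printed. None of the four is specified as a result, and no interval is planned for any of them.

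**The case against.** The best defence is that these analyses are optional and largely recoverable.

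- Protocol 9.7 opens with "Some tertiary (research) analyses may be done including", which governs the bullets below it, including the one worded as a commitment. There are no confirmatory objectives (protocol 9.9), and protocol 9.10 requires changes to be described and justified in the final report. This stands, and it limits the weight of the point. It does not explain why Section 8 lists other optional tertiary items and leaves these out.
- The reasons table reports frequencies as well as percentages, so the total number of visits will be visible. Total person-years are computed anyway (SAP 10.1.2.3), so a crude visit rate could be formed. This also stands. A reader might infer that the planned table would look the same whether few or many were hospitalised; the printed counts rule that out. What they do not give is the number of subjects, a rate as a planned result, or its interval.
- A reader might infer that regression was substituted for the symptom accuracy measures. The documents do not support that, since protocol 9.7 planned both side by side and the SAP simply kept one.
- The table shells cited in SAP 10.2 are not among the documents, so either analysis may already be programmed. That cannot be checked here.

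**Conclusion.** The point holds in a limited form. One part of one retained tertiary objective, the incidence of all-cause hospitalisation, has no specified analysis. One further set of measures named in protocol 9.7 is absent from the SAP, although partly derivable from 5.3.1. Section 8 records neither.

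A reader might go further and conclude that two study aims go unanswered. That is too strong. The reasons table answers the diagnosis part of the hospitalisation objective. The symptom accuracy measures are not an objective in themselves. The aim they serve, supporting future endpoint definitions, is still addressed by symptom frequencies, logistic regression, and the incidence of LCD with at least 3 days of fever and of hospitalised LCD.

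The primary and secondary objectives are unaffected. The conclusion rests on the SAP text without its table shells. The rates and predictive values shown are illustrations on assumed counts, and their exact Poisson intervals ignore household clustering.

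**What to change.** 1. In SAP 5.4.1, add the incidence of first hospitalisation for any cause: subjects hospitalised at least once, divided by person-years from enrolment to first hospitalisation, last contact or death, by the 9.2.1 rule, with a 95% CI. Keep the reasons table. If the 9.2.2 interval is reused, correct its upper limit first: as printed, (1 − α)/2 gives (1 − 0.05)/2 = 0.475, where the 0.975 quantile is needed.
2. In SAP 5.4.1, add sensitivity, specificity, PPV and NPV for LCD, each with a 95% CI, for each solicited symptom among AFI episodes with a valid RT-qPCR result.
3. If either analysis is deliberately dropped, list it in Section 8 with the reason.

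The cost is one or two descriptive tables from data already in the eCRF. No new collection is needed.
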